8.2 STATISTICAL ANALYSES

Subjects who received at least one dose of the vaccine will be included in safety assessments. Safety analyses will include summaries of the incidence of AEs using the NCI CTCAE Version 5.0 that occur during the study period regardless of causality. The AEs will be mostly descriptive initially. However, after unblinding at the completion of the study, rates of common side effects (occurring with 5% or more injections) will be compared between the PepCan and the placebo arms. Efficacy will be assessed by comparing cancer recurrence rate between the 2 arms. The expected number of head and neck cancer patients who achieve remission is 100 patients per year. For immunological assessments, the presence of new anti-HPV-16 E6 T-cell activity will be measured using CD3 ELISPOT assay, and its statistical significance will be assessed using a paired *t*-test. For analyses of immune cells such as Th1, Th2, Treg, and MDSCs, percentages before and after vaccination will also be assed using a two-tailed paired *t*-test. The frequencies between subjects who experience recurrence and those that do not in the PepCan arm will be compared using Wilcoxon rank-sum test. The diversity of gut microbiome will be assessed prior to

injection, and will be compared to that after injection using alpha diversity, beta diversity, and compositions at the phylum or family levels. These parameters will also be compared between subjects with and without recurrence with in the PepCan arm.

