1. PROTOCOL SUMMARY

1.1 SYNOPSIS

Title:	A Phase I/II Clinical Trial of PepCan in Head and Neck Cancer Patients in						
	Remission to Reduce Recurrence Regardless of HPV Status						
IRB Number:	217672						
Study Description:	This is a Phase I/II study to evaluate the efficacy and safety of an HPV therapeutic vaccine called PepCan (HPV-16 E6 peptides) in adults over a two (2) year period. Each subject will be receiving a total of 7 injections of PepCan (50 µg per peptide dose) or placebo (saline) at a 3:1 ratio in a randomized double-blinded design. Subjects will receive one injection every 3 weeks until they receive 4 injections. Then, subjects will receive one injection every 3 months until they receive a total of 7 injections. Subjects will have 2 more visits approximately 6 months apart after the last injection. Immunological assessment by enzyme-linked immunospot (ELISPOT) assay and by fluorescent activated cell sorter analysis (FACS) will be made at 4 time points (Visits 1, 5, 8, and 9). Stool samples will be collected at the Screening Visit, Visit 5, Visit 7 and Visit 8 for microbiome diversity analysis.						
Objectives: To evaluate the safety of a 7-injection regimen of Personal Secondary Objective: To evaluate the efficacy of a 7-injection regimen PepCan by observing cancer recurrence. Tertiary Objective: To evaluate the immunological response to PepCar Quaternary Objective: To analyze microbiome profile of DNA in su receiving PepCan.							
Endpoints:	Primary Outcome Measure: Safety of 7 dose regimen as defined by adverse events (AEs) after 2 years Secondary Outcome Measure: Efficacy of 7 dose regimen by clinically observing cancer recurrence Tertiary Outcome: Immunological responses assessed using ELISPOT assay and FACS analysis Exploratory Outcome: Profile of gut and oral microbiome before and after vaccination						
One hundred (100) subjects, 18 years of age or older, with a head and cancer diagnosis who have achieved complete remission, regardless of status							
Phase:	Phase I/II						

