Therefore, in this Phase I/II clinical trial of PepCan in subjects with head and neck cancer who achieved remission, the subjects in the vaccination arm will be given 7 doses of PepCan, so the duration of Th1 shift will be prolonged. The main goal would be to assess the safety and efficacy of giving 7 total doses of PepCan. For the assessment of efficacy, a randomized double-blind placebo-controlled design will be used in which the subjects will receive PepCan versus placebo at a 3:1 ratio. The first 4 doses will be given every 3 weeks, and the remaining 3 doses will be given every 3 months.

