2.4 RISK/BENEFIT ASSESSMENT

POTENTIAL RISKS

RISKS OF HPV PEPTIDES

No dose-limiting toxicities were observed in the Phase I trial. However, the total number of individuals who have received the vaccine is small, and there may be relatively rare complications that have not surfaced. The most common AEs were injection-site reactions, and none of the subjects experienced dose-limiting toxicities [36, 37]. Most commonly reported AEs were local swelling, redness, increased skin temperature, and local pain at injection sites. None of the vaccine-related events exceeded grade 2 according to the NCI CTCAE Version 4.0.

RISKS OF CANDIN®

Although the Candin® antigen is FDA-approved as a skin-test antigen for human use, the HPV peptide-Candin® (PepCan) combination has not been approved. According to the Candin® package insert, local reactions have included swelling, pruritus, and vesiculation. Immediate hypersensitivity reaction to Candin® has occurred in some individuals. Such reactions are characterized by edematous hives surrounded by a zone of erythema. They occur 15 to 20 minutes after intradermal injection. The safety of Candin® when used at a higher dose with increased frequency (up to 10 injections per subject) has also been demonstrated by the Phase I clinical trial of wart treatment we recently concluded [25]. The most common AEs were injection-site reaction with local swelling, redness, increased skin temperature, and local pain.

RISKS OF COMBINING HPV PEPTIDES AND CANDIN®

The safety of injecting the HPV-16 E6 peptides combined with Candin® was tested in the Phase I clinical trial of a human papillomavirus and appears to be safe [36, 37]. In the Phase I trial, subjects received a series of 4 doses of PepCan. Therefore, we do not anticipate any serious side effects when the number of injections is increased to 7 from 4.

STRATEGIES TO MINIMIZE RISKS

A pregnancy test will be performed prior to each vaccination in women of childbearing potential. All subjects will be asked to stay in the clinic for a minimum of 30 min after each injection to assure that immediate hypersensitivity reactions, if present, will be identified and treated appropriately. To ameliorate possible and anticipated localized minor vaccination site reactions, subjects will be offered a dose of ibuprofen or naproxen after a minimum of 30 min observation period.

POTENTIAL BENEFITS

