5.5 RECURRENCE

If a subject has clinical and/or radiological evidence of recurrence and a study physician determines the subject to be in recurrence, the subject will not receive further study interventions. The subject will be included in the recurrence group, and will complete participation by filling out the "Recurrence Questionnaire".

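### Section 8.2 plans no adverse-event analysis by injection number, and its 5%-of-injections rule can leave a late-dose reaction out of the arm comparison

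*Combined protocol and SAP*

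**What the plan says.** The primary outcome in the synopsis (Section 1.1) is "Safety of 7 dose regimen as defined by adverse events (AEs) after 2 years", and Section 2.3 states: "The main goal would be to assess the safety and efficacy of giving 7 total doses of PepCan".

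Earlier human exposure to PepCan was shorter. Section 2.4 reports: "In the Phase I trial, subjects received a series of 4 doses of PepCan". From this it infers that "we do not anticipate any serious side effects when the number of injections is increased to 7 from 4".

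Section 8.2 sets the safety population: "Subjects who received at least one dose of the vaccine will be included in safety assessments". Two analyses follow. One is "summaries of the incidence of AEs using the NCI CTCAE Version 5.0 that occur during the study period regardless of causality". The other, after unblinding, is that "rates of common side effects (occurring with 5% or more injections) will be compared between the PepCan and the placebo arms". The section mentions no table by injection number, no split between the first four and last three injections, and no count of subjects who received each injection.

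Not everyone will receive all seven. Under Section 5.5, once recurrence is determined, "the subject will not receive further study interventions". Sections 7.2 and 9.2 also stop injections after injection-related serious toxicity, and Section 9.2 does not replace withdrawn subjects.

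**The concern.** The trial should test Section 2.4's inference that going from four to seven injections brings no serious side effects. Within this trial, the data that bear most directly on it are the events after doses 5, 6 and 7, in the subjects who received them. The plan has no display that isolates those events or gives their denominator.

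The practical consequence lies in the selection rule. Section 8.2 compares arms only on side effects that reach 5% of injections. Counted over all seven injections, a reaction that becomes more frequent with repeated exposure is averaged with the earlier injections. It can fall below the threshold even when it is well above 5% at the added doses. The one between-arm safety comparison would then omit it.

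**Working it through.** **Inputs.** Section 8.1: two-year recurrence of 80% on placebo and 44% on PepCan; 75 and 25 subjects; about 5% dropout. Sections 6.2 and 7.1: injections on days 0, 21, 42 and 63, then every 3 months (91.3 days), so doses 5, 6 and 7 fall near days 154, 246 and 337.

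**The plan's own figure.** 80% × (1 − 0.45) = 44%. For a two-sided 5% test with 90% power and 3:1 allocation, the average proportion is (0.80 + 3 × 0.44)/4 = 0.53. The placebo number is [1.960·√(0.53 × 0.47 × 4/3) + 1.282·√(0.80 × 0.20 + 0.44 × 0.56/3)]² / 0.36² = 23.9. That gives 24 placebo and 72 PepCan, as stated. The calculation concerns recurrence; Section 8.1 gives no precision target for safety.

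**Subjects reaching each late dose.** The documents do not give the timing of recurrence. I assume a constant hazard from the first injection, so the share still on injections at day t is (1 − r)^(t/730.5).

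| Arm and two-year recurrence | Dose 5 | Dose 6 | Dose 7 |
|---|---|---|---|
| PepCan, 44% (of 75) | 66 | 62 | 57 |
| PepCan, 80%, no effect (of 75) | 53 | 44 | 36 |
| Placebo, 80% (of 25) | 18 | 15 | 12 |

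Spreading 5% dropout over two years gives 66/61/56, 53/43/35 and 18/14/12. With uniform recurrence timing, or 75% of recurrences in year 1, PepCan at 44% gives 68 or 64 at dose 5 and 60 or 52 at dose 7. Stops for toxicity are not counted.

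**Pooling across doses.** At 44%, doses 1–4 contribute 75.0 + 73.8 + 72.5 + 71.3 = 292.6 PepCan injections. Doses 5–7 contribute 66.4 + 61.7 + 57.4 = 185.5, which is 38.8% of the total. The plan does not say in which arm the 5% is counted; I apply it to PepCan. The per-injection rates below are illustrative and are not in the documents.

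- 2% early, 8% late: (292.6 × 0.02 + 185.5 × 0.08)/478.1 = 4.3%. At 80% recurrence it is 3.9%. With no attrition it is (300 × 0.02 + 225 × 0.08)/525 = 4.6%.
- 1% early, 8% late, at 44%: 3.7%.
- 3% early, 9% late, at 44% (with dropout): 5.3%, so this one would be selected.

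With a 2% early rate, the late rate must reach about (0.05 − 0.612 × 0.02)/0.388 = 9.7% before the pooled rate reaches 5%. Most of the dilution comes from mixing early with late doses; attrition adds to it.

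**Dose mix by arm.** At the design rates, doses 5–7 are about 39% of PepCan injections but 32% of placebo injections (44.2 of about 138). A pooled per-injection comparison would therefore set different dose mixes side by side.

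**Per-subject effect.** This is smaller. A 10% risk among subjects reaching dose 5 reads as 10% × 66/75 = 8.8% of all dosed at 44% recurrence, or about 7% at 80%. With no events, the one-sided 95% upper limit, 1 − 0.05^(1/n), is 3.9% for 75 subjects, 5.1% for 57 and 8.0% for 36.

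**The case against.** The case for leaving Section 8.2 alone has real force, and it rules out several stronger readings.

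- **A reader might infer that the one-dose population is the fault.** It is not. The set is conventional. Doses 1–4 are also new information here: by the counts in Section 2.1, Phase I gave about 16 women (6 + 10) the 50 µg dose, all aged 18 to 50. This trial takes adults of both sexes with no upper age limit, recently treated for cancer.
- **A reader might infer that only doses 5–7 are new.** The new population, just described, and the 3-month intervals are new too. Section 2.4 also reports up to 10 injections of Candin, though without the peptides.
- **A reader might infer that a late reaction would go unseen.** The incidence summary has no 5% threshold. In the 2%/8% example, assuming independent injections, about 24% of the 75 PepCan subjects would have the reaction, against 12% if the rate stayed at 2%. The summary would show that excess; what would be lost is the arm comparison.
- **A reader might infer that many subjects receive none of the added doses.** At the 44% design rate it is about 9 of 75 (12%). The loss is large only near 80%.
- **Pooling is not stated.** It is inferred from the per-injection threshold and the absence of any split.
- **Safeguards exist.** The individual and study stopping rules in Section 9.2 apply at any dose, and side effects are asked about since the last injection, so a by-dose table could be made later.
- **Late-dose tables select survivors.** Subjects who recurred or stopped for toxicity are gone by then.

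All of these stand as limits. They do not remove the gap. Followed as written, the selection rule can exclude a late-dose reaction from comparison, and a by-dose table chosen after unblinding would be weaker evidence than a prespecified one.

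**Conclusion.** The point holds in a limited form. The primary objective concerns seven injections, but Section 8.2 plans no AE analysis by injection number, and its threshold is not split by dose. An illustrative side effect at 2% early and 8% late pools to between 3.9% and 4.6% across the attrition cases shown, so it would miss the arm comparison while still appearing in the AE summary.

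The subject counts rest on Section 8.1's recurrence rates and an assumed constant hazard. The pooled rates rest on illustrative inputs and on reading the threshold as covering all seven injections together. The documents do not support a claim that a late-dose signal would be concealed altogether or that the safety population should change. This is a worthwhile, inexpensive improvement to the analysis plan.

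**What to change.** In Section 8.2:

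1. Keep the at-least-one-dose population and overall AE incidence as the main safety display.
2. Add a prespecified supplement by arm: the number injected at each dose, and AE incidence by injection number (1 to 7) and for doses 1–4 versus 5–7. The denominator is the subjects who received that injection (for a block, at least one injection in it), with exact 95% intervals.
3. Apply the 5% selection rule within doses 1–4 and within doses 5–7 as well as overall, and say in which arm the 5% is counted.
4. State that late-dose and seven-dose-completer tables describe subjects who neither recurred nor stopped for toxicity, and show stops for toxicity by dose number beside them.

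No new data are needed: Section 7.1 asks about side effects since the last injection, and Section 7.4 records event start dates. The cost is a few extra tables. Survivor selection in the late-dose rows remains, and the placebo intervals there will be wide: with no events in 12 subjects, the exact two-sided 95% upper limit is 1 − 0.025^(1/12) = 26%.

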3. OBJECTIVES AND ENDPOINTS

OBJECTIVES	ENDPOINTS	JUSTIFICATION FOR ENDPOINTS
PRIMARY		
Determine the safety of a	Careful monitoring of adverse events	Investigators will use NCI CTCAE
7-injection scheduling of	(AEs) at all ten (10) visits (2 years)	Version 5.0 to assess AEs and
PepCan regimen.	based on NCI CTCAE Version 5.0.	evaluate the safety of PepCan.
SECONDARY		
Determine the efficacy of	The absence of recurrence will be	The goal of PepCan vaccine is to
a 7-injection PepCan	assessed at all ten (10) visits (2 years).	reduce recurrence of head and
regimen.	Recurrence rates will be compared	neck cancer.
	between the PepCan and placebo arms.	
TERTIARY		
Determine immunological	T-cell (ELISPOT assay) and immune	Immunological responses are
responses to a 7-injection	regulatory cell responses (FACS	important in preventing cancer
PepCan regimen.	analysis) at Visits 1, 5, 8, and 9 will be	recurrence.
	assessed before and after vaccination.	
EXPLORATORY		
Compare the profile of	DNA sequencing methods will be	Diversity of gut microbiome is
gut and oral microbiome	utilized. Stool samples will be analyzed	now recognized to be associated
before and after PepCan	after Screening Visit, and Visits 5, 7, and	with favorable response to
regimen.	8. Oral wash samples will be analyzed at	cancer immunotherapy [27].
	Screening Visit, and Visits 5, 7, and 8.	

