8. STATISTICAL CONSIDERATIONS

8.1 DETERMINATION OF SAMPLE SIZE

The recurrence rate of head and neck cancer is 80% over 2 years (50 to 60% local recurrence and 20 to 30% distant recurrence [41]. In the Phase I trial of PepCan described above the overall histological regression rate of HSILs was 45% [36]. A reduced recurrence rate by the magnitude of 45% would reach 44%. Vaccinating 72 subjects in the PepCan arm and 24 subjects in the placebo arm would have 90% power at alpha of 5%, 2 tailed. Accounting for about 5% drop out rate, 75 subjects would be needed in the PepCan arm, and 25 subjects in the placebo arm.

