If at any point in the study, $\geq 10\%$ of subjects experience injection-related serious toxicity, the study enrollment and injections will be suspended. These activities can only re-start after notifying the applicable regulatory agencies and with a permission to resume from the Medical Monitor and Sponsor.

The study enrollment and injections will be suspended if any subject experiences vaccine-related Grade IV or higher AE. These activities can re-start only after notifying the applicable regulatory authorities and with a permission to resume from the Medical Monitor and Sponsor.

If the study is prematurely terminated or suspended, the UAMS PI will promptly inform study subjects, the IRB, and Sponsor and will provide the reason(s) for the termination or suspension. Study subjects will be contacted, as applicable, and be informed of changes to study visit schedule. If only suspended, the study may resume once all concerns have been addressed, and satisfy the Sponsor, IRB and/or the FDA.

EMERGENCY UNBLINDING

If a medical emergency necessitating the identity of the injection administered occurs, the local site PI or a local Sub-Investigator will notify the sponsor and UAMS PI. The UAMS PI will be available 24 hours, 7 days a week, and if the medical emergency occurs after hours the UAMS PI should be notified via the afterhours number listed on the protocol title page. After permission is given to unblind by the UAMS PI, local site pharmacy will identify the injection to the requesting investigator and Study Coordinator, and note any incidence in the Randomization book. UAMS PI will notify the medical monitor if necessary for further review.

LOST TO FOLLOW-UP

A subject will be considered lost to follow-up if he or she fails to return for two (2) consecutive scheduled visits and is unable to be contacted by the study site staff.

The following actions must be taken if a subject fails to return to the clinic for a required study visit:

- The site will attempt to contact the subject and reschedule the missed visit as soon as possible and counsel the subject on the importance of maintaining the assigned visit schedule and ascertain if the subject wishes to and/or should continue in the study.

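### The only stated between-arm safety comparison is limited to events seen with at least 5% of injections, so a once-only reaction in about a fifth of PepCan subjects would not be compared with placebo

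*Combined protocol and SAP*

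**What the plan says.** The primary objective in Section 3 is the safety of the seven-injection regimen; its endpoint is "Careful monitoring of adverse events" at all ten visits. Section 8.2 then sets out two layers of safety analysis.

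- A summary layer: "Safety analyses will include summaries of the incidence of AEs" regardless of causality, with no frequency threshold. The text adds that "The AEs will be mostly descriptive initially". It does not say that these summaries are split by arm.
- A comparative layer, after unblinding: "rates of common side effects (occurring with 5% or more injections) will be compared between the PepCan and the placebo arms". No test is named. The text does not say whether the 5% is taken over PepCan injections, over each arm, or over both arms pooled.

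No other between-arm safety comparison appears in the document. The synopsis gives the exposure ("Each subject will be receiving a total of 7 injections of PepCan" or placebo), and Section 8.1 gives the arm sizes ("75 subjects would be needed in the PepCan arm, and 25 subjects in the placebo arm"). By contrast, the study stopping rule in Section 9.2 counts subjects: once at least 10% "of subjects experience injection-related serious toxicity, the study enrollment and injections will be suspended".

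**The concern.** The threshold decides which adverse events are ever set against placebo. Because it is a rate per injection, an event that happens once in a subject is diluted by up to a factor of seven. A reaction common enough to matter to patients, and different enough between arms for this trial to detect, can fall below the line.

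The threshold also becomes stricter as the regimen lengthens. The background section and Section 7.4 report Phase I events at the same 5% of injections, on a four-injection regimen. For once-only events, 5% per injection meant 4 × 5% = 20% of subjects there; it means 7 × 5% = 35% here. No reason is given for carrying the figure over.

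At stake is the use of the placebo arm for the primary endpoint. If the list of compared events is widened only after unblinding, the choice will be post hoc.

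**Working it through.** **Inputs.** 75 PepCan and 25 placebo subjects (8.1); seven injections each (synopsis, 6.2); cut-off 5% of injections (8.2); two-year recurrence of 44% on PepCan (8.1); injections stop at recurrence (5.5) and at injection-related serious toxicity (7.2, 9.2).

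**The plan's own figure.** The 5% cut-off has no derivation to reproduce. The arm sizes do. For 80% against 44% with 24 and 72 subjects, the pooled proportion is (3 × 0.44 + 0.80)/4 = 0.53.

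- SE under the null = √(0.53 × 0.47 × (1/72 + 1/24)) = 0.1176
- SE under the alternative = √(0.44 × 0.56/72 + 0.80 × 0.20/24) = 0.1004
- z = (0.36 − 1.96 × 0.1176)/0.1004 = 1.29, so power is 90%, as stated
- Dropout: 72/0.95 = 75.8 and 24/0.95 = 25.3, in line with 75 and 25

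**A once-only reaction in 15 of 75 PepCan subjects (20%).**

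| Exposure | Injections | 15 events as a share |
|---|---|---|
| All doses given, PepCan | 75 × 7 = 525 | 2.9% |
| Dosing stops at recurrence, PepCan | 75 × 6.374 = 478 | 3.1% |
| Affected subjects stop after dose 1, PepCan | 15 + 60 × 7 = 435 | 3.4% |
| Both of the above, PepCan | 15 + 60 × 6.374 = 397 | 3.8% |
| All doses given, both arms pooled | 100 × 7 = 700 | 2.1% |

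The mean of 6.374 injections assumes exponential recurrence from the first dose to 44% at 104 weeks, with doses at weeks 0, 3, 6, 9, 22, 35 and 48. The event is below 5% in every row.

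**Could the trial see it?** The two-sided Fisher test of 15/75 against 0/25 gives p = 0.019. Exact Fisher power at 75/25 is 84% for 20% against 0%, 43% for 20% against 4%, and 20% for 20% against 8%.

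**Where the cut-off bites, for once-only events.**

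- PepCan denominator, full dosing: 0.05 × 525 = 26.25, so 27 events, 27/75 = 36% of PepCan subjects.
- Pooled denominator, full dosing, event on PepCan only: 0.05 × 700 = 35 events, 35/75 = 47%.
- PepCan denominator, every affected subject stops after dose 1: x/(x + 7(75 − x)) ≥ 0.05 gives 1.3x ≥ 26.25, so x = 21, 21/75 = 28%.

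**Events at the level of the suspension rule.** Take ten subjects in 100, with one serious toxicity each.

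- All doses counted: 10/700 = 1.4%.
- All ten stop after dose 1, both arms: 10/(10 + 90 × 7) = 10/640 = 1.6%.
- All ten on PepCan and stopping after dose 1, PepCan denominator: 10/(10 + 65 × 7) = 10/465 = 2.2%.

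So a class of events that suspends the trial would not qualify for comparison under any of these counts.

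**The case against.** The strongest defence is that the gate restricts a supplementary comparison, not the safety evaluation itself. The synopsis says safety is assessed descriptively, 8.2 summarises all adverse events without a threshold, and serious events are covered by the stopping rules, medical monitor review and expedited reporting. The cut-off also matches Phase I reporting, which helps continuity. All of that is true. But the summaries are not committed to be by arm, and stopping rules and expedited reports do not supply a contrast with placebo.

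The defence is also right on power. At 10% against 0%, exact Fisher power is only 7%, and 10/75 against 0/25 gives p = 0.062. At suspension level the gain is therefore an estimate by arm with its interval, not a useful test. The 84% figure needs no placebo events at all.

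Three stronger readings are tempting and are not supported.

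- A reader might infer that a reaction in a third of PepCan subjects could never be compared. With full dosing, 25/525 = 4.8% does miss. Under the plan's own 44% recurrence, 25/478 = 5.2% qualifies on the PepCan denominator.
- A reader might infer that only injection-site reactions would qualify. The Phase I list at this cut-off also contains myalgia, headache, nausea, fatigue, hypokalemia, fever and flu-like symptoms.
- A reader might infer that the choice of denominator is immaterial. For a PepCan-only event it moves the bar from 36% to 47% of PepCan subjects.

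**Conclusion.** The point stands. Followed as written, 8.2 leaves a once-only reaction in about a fifth of PepCan subjects outside the only stated between-arm safety comparison. Its rate is 2.9% to 3.8% of PepCan injections in the scenarios computed, and lower on a pooled denominator with full dosing. Yet a 15/75 against 0/25 split would be nominally significant. Once-only events need to reach 36% of PepCan subjects to be compared with full dosing, about 28% if every affected subject stops after dose 1, and 47% on a pooled denominator with full dosing.

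The result assumes one event per affected subject and, for the p-value, no placebo events. Repeated events reach the cut-off at lower subject frequencies. The recurrence-adjusted figures rest on exponential timing and 13-week spacing for three months, neither of which is in the documents; the conclusion for a fifth of subjects does not depend on them. This should be changed before unblinding, but it does not undermine safety monitoring during the trial.

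**What to change.** In Section 8.2:

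1. Present and compare by arm the proportion of subjects with at least one event, for each adverse event term reported in at least 5% of subjects in either arm, and name the test (Fisher's exact test would match Section 7.3).
2. Regardless of frequency, show by arm, with exact confidence intervals, events meeting the Section 7.2 serious-toxicity definition, Grade III or higher events, and SAEs.
3. Keep per-injection rates as a descriptive supplement for continuity with Phase I, with the denominator defined.

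This needs no new data, visits or subjects, only SAP wording and additional table rows. The downside is more adverse event comparisons. The plan should say that they are read descriptively, without multiplicity control. The 5%-of-subjects line is itself a convention, which is why item 2 carries no threshold.
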